1. INTRODUCTION

Anterior cruciate ligament (ACL) reconstruction is one of the most common orthopaedic procedures performed among young, active and healthy individuals [9]. The incidence of this operation in Norway is reported to be 85/100,000 in the younger population [9]. However, reports state that there is a subset of patients that remain unstable after reconstruction and almost forty percent of the reconstructed patients are unable to regain their prior function [2]. Long term, more than 50% of ACL reconstructed patients develop radiographic signs of osteoarthritis [21]. The double-bundle ACL reconstruction technique was developed to improve both the anatomical and biomechanical properties of the knee after the reconstruction, due to the restoration of both of the bundles of the ACL: the anteromedial (AM) and the posterolateral (PL) bundle [31]. Their different insertion sites and tension patterns during knee motion, were supposed to resemble the native ACL more closely than the traditional single-bundle reconstruction. Although many laboratory studies support these findings, clinical studies are less convincing [18, 27, 31-33]. It has also been questioned whether these improvements are able to justify the loss in cost-effectiveness by adopting to this technique [5]. Large, high-quality studies, with focus on the patient's subjective outcome has been requested in order to decide if double-bundle reconstruction technique should continue to be an option for the ACL injured patients [1, 12, 16, 25].

This study was designed to compare the double-bundle to the single-bundle ACL reconstruction with focus on patient reported outcome measurements [30].

2. STUDY OBJECTIVES

2.1. Primary objective

The main objective of this study was to compare the Knee Osteoarthritis Outcome Score (KOOS) Quality of Life (QoL) subscale, two years after the operation between two different surgical techniques for primary ACL reconstruction: the anatomic double-bundle and the anatomic single-bundle ACL reconstruction.

We hypothesised that the anatomic double-bundle procedure would result in an improved KOOS QoL subscore, two years postoperatively, compared to the anatomic single-bundle ACL reconstruction technique.

2.2. Secondary objectives

Secondary objectives were to compare the other patient reported outcome measurements, functional tests, results from the clinical examination and radiographic imaging (Kellgren-Lawrence standing radiographs) of the double-bundle and single-bundle reconstructions, one and two years postoperatively.

Patient reported outcomes :

- 1) the remaining 4 KOOS subscales:

Pain

Symptoms
Activities of daily living (ADL)
Sports and Recreation

2) the subjective International Knee Documentation Committee form (IKDC 2000)

3) the Sports activity scales and return to sport questionnaires:

Tegner activity scale
Sports Activity Scale
Return to previous attended main sports

Clinical examination:

4) Knee laxity test:

Lachmann's test
Pivot shift test
KT-1000 arthrometer (Knee Laxity Testing Device)

5) Knee joint range of motion (ROM):

Flexion deficit
Extension deficit

Functional performance test:

8) One leg hop test

Radiographic imaging:

9) Kellgren-Lawrence classification grade 1- 4 using standing anterior-posterior (AP) radiographic imaging in a Synaflexer™ X-ray positioning frame (Synarc Inc, San Francisco, CA, USA).

Adverse Events:

10) Postoperative adverse events:

Bleeding/hematoma.
Deep venous thrombosis (DVT)
Nerve or arterial injury
Infection

Arthrofibrosis
Cyclops
Donor site morbidity

11) New injuries:

New meniscus injury
New cartilage injury
Graft re-rupture

12) Reoperations and revision surgery.

3. STUDY METHODS:

3.1. Study design:

The study was designed as a prospectively randomised, controlled, superiority study, following two parallel groups with a 1:1 allocation ratio. The intervention group was the anatomic double-bundle ACL reconstruction and the control group, anatomic single-bundle ACL reconstruction.

3.2. Study settings:

The protocol was published at ClinicalTrials.gov at 15th Dec 2009 (Clinical trials ID: NCT01033188). The inclusion period was from 01.01.2010 until 18.06.2015. The follow-up was performed at 12 and 24 months (1 and two years) after index surgery. The study was completed with the two-years follow-up of the last patient on 17th June 2017.

The patients were recruited from the outpatient clinic at Oslo University Hospital during the entire inclusion period. From March 1st, 2013 Martina Hansens Hospital was added as recruitment hospital. Initially, the interventions were performed at Oslo University Hospital. From March 1st, 2013 until end of inclusion, the site of intervention was changed to Martina Hansens Hospital. Both hospitals perform more than 100 ACL reconstructions yearly and recruit patients from a rural environment. A single surgeon performed the surgery at all study participants except two in both hospitals. The surgeon was experienced and instructed in how to perform the intervention, prior to inclusion of the first patient.

Collection of baseline information was conducted after a minimum of two months of rehabilitation and within three months before the operation. The 1 and the two-years follow-up, was performed within three weeks from the examination date. Patients responses obtained outside of these time frames will not be considered in the per protocol analysis. In the intention to treat (ITT) analysis all collected data at each time point will be considered. The average time until the examination was recorded in both groups for one and two years.

3.3. Inclusion and exclusion criteria:

Inclusion criteria:

The participants had to comply with the following at randomization:

- 1) Age from 18 to 40 years.
- 2) Symptoms from their knee due to a primary ACL injury
 - verified by history,
 - clinical assessments (Lachman >1+ and/or positive Pivot shift test)
 - and identified under surgery
- 3) Successfully completed a preoperatively 3 (minimum 2) months of ACL rehabilitation program supervised by a physiotherapist.

Exclusion criteria

- 1) A previous ACL reconstruction in the involved knee.
- 2) A subtotal (partial) ruptured ACL.
- 3) PCL, LCL or PLC injury.
- 4) Increased medial, lateral or posterolateral ligament laxity at the operating table, compared with the uninvolved leg.
- 5) ACL injury of the uninvolved knee.
- 6) Less than 50% of one of the menisci preserved after surgical treatment.
- 7) Established osteoarthritis (Kellgren-Lawrence classification grade 3 or 4) identified at the baseline standing front radiographs of the knee.
- 8) Hamstring tendons with insufficient graft thicknesses after preparation (defined as less than of 5.0 mm in diameter for the PL, and 6.0 mm for the AM bundle).
- 9) Patients living outside recruitment area, and patients who could not understand the Norwegian written language.

3.4. Flow chart: Table 1

4. INTERVENTIONS:

The surgical technique consisted of the patient in supine position, with the knee at 90 degrees of flexion and with a tourniquet placed around the upper thigh. The establishment of the regular anterior arthroscopic portals was obtained. The ACL lesion was confirmed by visualization and by probing the ACL remnants, and a further debridement of the residual ACL stump and footprints was performed. The femoral and tibial insertion site was visualized, and surrounding soft tissue and bony landmarks were used to identify the centre of the proximal and distal ACL footprint [33]. A 3-5 cm skin incision was performed at the pes anserine insertion site. The semitendinosus and gracilis tendons were identified. A tendon harvester was used to free the tendons, and then they were doubled or tripled according to their length and thicknesses. For the double-bundle operation technique, a minimum graft size of 5.0 mm in diameter for the posterolateral (PL), and 6.0 mm for the anteromedial (AM) bundle was desirable. Both ends of each the grafts were whip stitched with a non-absorbable suture. The drillguide diameters were chosen as close to the graft diameter as possible, in both techniques.

4.1. Single-bundle reconstruction:

An accessory anteromedial portal was used for the femoral tunnel establishment. A Steadman awl was positioned in a central position of the femoral footprint, targeting to have the tunnel covering both parts of the AM and PL bundle attachment sites. With the knee in hyperflexion, a guide pin was inserted at the same position, and over-reaming of the guide pin was performed, according to measured graft size. With an external tibia guide, the center of the tibial tunnel was positioned according to remaining soft tissue and bony landmarks[33]. The tibia guide pin was aimed towards the tibia guide aimer and over-drilled relative to the distal graft size. The graft was passed through the tibial and then the femoral tunnel, and graft fixation on the femoral side was obtained with a suspension device (Endobutton CL™, Smith & Nephew, London, United Kingdom). The graft was cycled through 20 flexion-extension movements. The tibial fixation was then realized with the knee at 20 degrees of flexion and under manual tensioning, with a non-absorbable PEEK interference screw (Biosure PK™, Smith & Nephew, London, United Kingdom) placed eccentrically to the graft.

4.2. Double-bundle reconstruction:

An accessory anteromedial portal was used for the femoral tunnel establishment. The centre of the PL and then the centre of the AM bundle was marked with a Steadman awl. A prefabricated double-bundle femoral drill-guide (Acuflex Pin Point™, Smith & Nephew, London, United Kingdom) was used to drill the femoral tunnels. The posterolateral tunnel was drilled first, then anteromedial tunnel was drilled in sequence, through the accessory anteromedial portal with the knee in a hyperflexion position. On the tibial side, using the prefabricated double-bundle tibia guide (Acuflex Pin Point™, Smith & Nephew, London, United Kingdom) the centre of the AM and then the PL tunnel was aimed at with the two guide pins [33]. The guide pins were overdrilled relative to the distal graft sizes. The grafts were passed through the tibia and then the femoral tunnel and fixation on the femoral side was realized with one suspension device for each tunnel (Endobutton CL™, Smith & Nephew, London, United Kingdom). The knee was cycled through 20 flexion-extension movements, and under manual tension first the AM bundle was fixated at 60 degrees flexion, then the PL bundle was fixated with the knee at full extension. Both tibial fixations were achieved with an eccentric placed PEEK interference screw (Biosure PK™, Smith & Nephew, London, United Kingdom).

Notchplasty was only realized if graft impingement was detected after graft insertion. Measurements of the insertion sites were performed if there were any doubt about the patient having a sufficient notch size, but not as a routine. The wounds were closed and bandaged before the tourniquet was loosened. Free mobilization was achieved from the first postoperative day without brace support or the use of a CPM.

5. ANALYSIS SETS

5.1. Full analysis set (intention to treat; ITT):

All subjects randomised to either one of the two treatment arms, who completed the baseline assessment; independent of the actual intervention they received and whether the assessments at all time points were completed.

5.2. Per protocol (PP) analysis set:

All subjects that received the treatment to which they were randomised, and fulfilled all the required assessments at baseline and at the two-years follow-up.

Exclusion criteria from the PP set:

- Patients that did not receive the treatment they were randomised to get.
- Patients that did not complete the baseline and two years assessments of the KOOS QoL subscale.
- Patients with an ACL revision procedure performed before the two-years follow-up. (They were not excluded if the revision surgery was more than two years after index surgery even if they were identified with graft rupture.)
- Patients lost to follow-up.

6. SPECIFICATION OF OUTCOME

The primary outcome KOOS QoL subscale and all secondary outcomes will be analysed as the ITT set. Secondary analyses will be performed as PP set for the primary outcome and the remaining 4 KOOS subscales: Pain, Symptoms, Activity of daily living and Sports and recreation.

6.1. Primary outcome:

The primary outcome of the study is the difference between the two treatments as mean change of the KOOS QoL subscore from baseline to the two-years follow-up.

6.2. Secondary outcomes:

The difference between the two treatments in the following outcomes:

1. The mean change in the **KOOS Symptoms** subscore from baseline till two years.
2. The mean change in the **KOOS Pain** subscore from baseline till two years.
3. The mean change in the **KOOS Activities of Daily Living** subscore from baseline till two years.
4. The mean change in the **KOOS Sports and Recreation** subscore from baseline till two years.
5. The mean change in the **IKDC 2000 subjective score** from baseline till two years.
6. Knee laxity as measured by the **Lachman's test** at two years.
7. Knee laxity as measured by the **Pivot shift test** at two years.
8. Knee laxity as measured by the **KT-1000** at two years.
9. Range of motion as measured by the mean **extension deficit** in the involved knee compared to the uninvolved knee at two years.
10. Range of motion as measured by the mean **flexion deficit** in the involved knee compared to the uninvolved knee at two years.
11. The **Tegner activity score** at two years.
12. The **Activity Scale level** at two years.
13. **Return to sports** at two years.
14. The mean change in the **One leg hop test** from baseline till two years.

15. The degree of degeneration in the involved and uninvolved knee, classified by the **Kellgren-Lawrence** classification system, at two years.
16. The number of **Adverse events** including bleeding, DVT, infection, donor site pain, arthrofibrosis or cyclops within two years after the operation.
17. The number of new **menisci injuries** at two years.
18. The number of new **cartilage injuries** at two years.
19. The number of **ACL graft re-ruptures** at two years.
20. The number of **Reoperations** within the two-years follow-up.

Secondary outcome derived from the primary outcome

21. The difference between the two treatments in **subjective treatment failures**, defined as KOOS QoL subscore < 44 point

7. STUDY VARIABLES

7.1. Study variables assessments:

| | Preinjury (retrospective) | Baseline | 1 year | 2 years |
|--|------------------------------|----------|--------|---------|
| History Examination | | X | X | X |
| Weight / Height | | X | X | X |
| Activity/sport participation | X | X | X | X |
| PROMS: KOOS IKDC 2000 Tegner activity score Activity scale | X | X | X | X |
| Functional tests | | X | X | X |
| Objective tests: ROM, Pivot , Lachmann, KT 1000 | | X | X | X |
| Radiographic imaging x-ray | | X | X | X |
| Associated injuries and Additional surgery | | X | | |
| Adverse events Re-injuries and Reoperations | | | X | X |

7.2. Patient related outcome measurements:

7.2.1. KOOS:

The KOOS was developed to evaluate both short- and long-term outcome after knee injuries in young and active subjects with a knee injury or osteoarthritis in their knee[23]. It is proven as a reliable, valid and responsive score for patients undergoing ACL reconstruction[6, 24]. The KOOS data are obtained from a questionnaire, where five dimensions are rated separately: Pain, Symptoms, Activity of daily living, Sports and recreation and Quality of life. The five different subscores have different effect sizes reflecting knee function, symptoms and expectations on an individual basis. It is therefore desirable to interpret them separately, and an aggregated score of all five subscales will not be calculated [23].

The minimal perceptible clinical improvement (MPCI), has not been formally assessed for the KOOS, although the 8-10 points change in one subscore has been used as a clinically meaningful change following ACL reconstruction [23].

The primary outcome of this study was the KOOS QoL subscale. This subscale is considered to be the most sensitive and responsive among the five dimensions of the score for ACL injured patients[6].

The four remaining subscales would be considered as additional supportive variables to the primary outcome. The five KOOS scales include 42 items with different numbers of elements within each subscore (4-11). Each item can score on a scale from 0 - 4. The five subscales are separately calculated, ranging from 0-100 points where 100 point is the best score possible.. At least 50% of the items within each subscale must be responded to before the score is calculated.

Scale: 0-100 points in each subscale.

Assessment: Baseline, one- and two-years follow-up.

7.2.2. IKDC 2000 subjective scale:

The IKDC 2000 was developed by the International Knee Documentation Committee (IKDC), as a standardized form, for different knee conditions. The original score contents of both clinical assessments, pathology identified during surgery and the subjective IKDC score. The subjective score contains only the patient administered form of the total score. The score includes 18 different items that cover three domains: Symptoms, sports, and current knee function. Each item is weighted according to its importance on the total score, and the worst score in each category is carried forward. Range 0-100 points. (A total score of 100 points =normal sports participation with absence of symptoms and no limitation in the daily activity [10, 14]).

Scale: 0-100

Assessment: Baseline, one- and two-years follow-up.

7.2.3. Tegner activity scale:

The score was developed complementary to the Lysholm score, to detect whether loss in function could be masked by the level of activity [28]. The score is graduated in 11 different levels of activity (0-10), from recreational to competitive sports. Level 0 indicates the lowest knee-related activity (sick leave or disability), and 11 the highest knee related activity (competitive sports at a national level).

Scale: 0-10.

Assessment: Before injury, baseline, one- and two-years follow-up.

7.2.4. Sports Activity Scale:

The Activity Scale was based on one of the subjective assessments included in the Cincinnati Knee Rating System and is a self-administered score that detects the level of sports activity [4]. The original score contains four different levels of sports frequency. Within each level there is a grading from sports performed with "no running, twisting or jumping"(cycling/swimming), to sports with "hard pivoting, cutting, jumping"(basket, football).

In this study, only the frequency of sports participation was recorded in the scale, with four different levels frequency (1=sports performed less than one day per month, 4= sports performed more than 4 days per week).

Scale: 1-4.

Assessment: Before injury, baseline, one- and two-years follow-up..

7.2.5. Return to sports:

The patients recalled the two main sports they participated in, the year ahead of the ACL injury.

Return to sports was defined as the return to one of the two main sports after the ACL reconstruction was performed. If the same sport was recorded in one of the two follow-ups, the patient was defined as having returned to sports.

Scale: yes (y) or no (n).

Assessed: Before injury, baseline, one- and two-years follow-up..

7.3. Clinical testing:

7.3.1. Lachman's test:

The Lachman's test is a reliable manual laxity test to distinguishing an ACL rupture from an intact ACL. The test has been found to have a higher sensitivity and specificity compared to other manual tests for ACL injury[8, 17]. The test can be graded similarly to the anterior drawer test and is carried out with the patient in supine position and 20 degrees of flexion in the involved leg. One hand is stabilizing the femur and the other hand performing a subluxation of the tibia in the anterior direction. The anterior displacement is recorded in mm and always reported as the difference to the contralateral leg[10].

Grade 3+ = >10mm displacement of the tibia compared to the uninvolved leg

Grade 2+ = 5-10mm

Grade 1+ = 3-5 mm

Grade 0= 0-3mm

Scale: 0-3

Assessment: Baseline, one- and two-years follow-up.

7.3.2. Pivot shift test:

The Pivot shift test is known as a pathognomonic test for the ACL insufficient knee. The phenomenon is described as the reduction of the tibia from a subluxated position as the knee is extended with the tibia internally rotated [11, 20]. The Pivot shift phenomenon can be graded on a scale from 0 to 3+[15, 26] according to the amount of subluxation of the tibia and its the reduction in extension. There has been a discussion among the experts whether a positive test should be recorded as such, or if it should be compared to the contralateral leg.

In this study the Pivot shift was detected by the Slocum`s test and not compared to the contralateral leg[26].

Pivot shift:

Grade 0

Grade +1= “trace” positive only in medial/internal rotation of the tibia

Grade +2= “clunk” subluxation in neutral positioning of the tibia

Grade+3= “gross” subluxation in any rotation, laxity due to secondary restraints additional to the ACL injury or in chronic unstable knees.

Scale: 0-3.

Assessment: Baseline, one- and two-years follow-up.

7.3.3. KT-1000

The KT-1000™ (MEDmetric, San Diego, CA, USA) (Knee Laxity Testing Device), is an instrument detecting knee laxity in the anteroposterior direction[7]. It has two sensor pads that are placed in contact with the patella and the greater tuberosity of the tibia during an instrumented Lachman's test of the knee. The instrument detects the motion between those two sensor pads during anterior translation of the tibia towards the femur. Displacements at loads of 134 N and maximal manual load (MM) are detected. Displacement in the involved compared to the uninvolved knee will be detected[7].

Range: - 20 till +20mm.

Assessment: Baseline, one- and two-years follow-up..

7.3.4. Range of motion (ROM)

As the knee joint is a hinge joint, the range of motion can be detected as both the extension/flexion movement and by internal/external rotation[11]. In this study, only the extension/flexion movements are detected. The normal flexion is widely individual from 120-150 degrees, and therefore the flexion deficit was compared to the uninvolved knee. If any extension- or flexion-deficit was detected, a goniometer was used for exact measurement of the deficit and recorded. The extension deficit of the involved knee was compared both to 0(zero) degrees of extension and to contralateral knee extension.

Scale:

Extension: -20 (hyperextension) to 150 degrees

Flexion: 0-150 degrees.

Assessment: Baseline, one- and two-years follow-up.

7.4. Functional performance tests:

The functional tests were performed to evaluate the functional capacity of the knee. The tests reveal both the clinical assessments and the patient's perception of their knee.

7.4.1. One leg hop test

The "one leg hop test" is a functional test often used as part of a performance test for ACL deficient knees[20, 29]. It is known to be highly correlated to the clinically assessed instability of the knee[3]. The test was performed with two attempts at each leg, the best of the two scores were documented and the percentage difference from the uninjured knee presented:

Operated knee hop distance/Non operated knee hop distance X 100

Scale: 0-100 %.

Assessment: Baseline, one- and two-years follow-up.

7.5. Radiographic imaging:

Radiographic imaging was performed with a single, standardised, front standing radiograph of both legs. Both legs were classified according to the Kellgren-Lawrence grading system of osteoarthritis in the joint[19].

Kellgren Lawrence classification[19]:

Grade 0: no radiographic features of OA are present

Grade 1: doubtful narrowing of joint space and possible osteophytic lipping

Grade 2: definite osteophytes and possible narrowing of joint space

Grade 3: moderate multiple osteophytes, definite narrowing of joint space and some sclerosis and possible deformity of bone ends

Grade 4: large osteophytes, marked narrowing of joint space, severe sclerosis and definite deformity of bone ends

Scale 0-4.

Assessment: Baseline, one- and two-years follow-up.

7.6. Adverse events, new injuries and reoperations:

Adverse Events:

Any observed bleeding or excessive hematoma during the first 6-8 weeks after the operation.

Deep venous thrombosis (DVT), nerve or arterial injury in the involved leg.

Infection including both superficial infection and septic arthritis of the involved joint.

Arthrofibrosis, cyclops with or without extension deficit in the involved knee.

Donor site morbidity due to fixation device, scar tissue or to the hamstrings tendon harvesting in involved leg.

New injuries:

New menisci injury detected after the intervention either by MRI or verified by second look arthroscopy. The injuries were further differentiated into medial and lateral menisci injuries and into the treatment they accomplished (resection, suture or transplantation).

Any new cartilage injury detected after the intervention.

ACL Graft reruptures defined as a total rupture of the ACL reconstruction, found at clinical examination and MRI or second look arthroscopy.

Reoperations:

Reoperations because of hematoma, nerve or arterial injury, infection, arthrofibrosis, cyclops or donor site morbidity.

Menisci surgery including suturing, resection or transplantation.

Reoperations due to cartilage surgery.

Re-arthroscopy due to other reasons.

Revision surgery because of graft rupture, both first and second stage revision surgery.

8. SAMPLE SIZE CALCULATION:

The sample size was calculated as for a superiority study, based on the null hypothesis that quality of life following double-bundle ACL reconstruction is equal to KOOS quality of life following single-bundle ACL reconstruction.

The primary outcome, KOOS QoL subscale, was used for the sample size calculation. A minimal important change (MIC) in QoL of 8 points, has been considered sufficient [23]. With equal allocation in both arms, a standard deviation of 15 points, power of 80%, and assuming a two-sided significance-level of 0.05, the sample size was calculated to be 56 patients in each treatment group.

To allow for 5% drop-outs, the final sample size was set to be 60 patients in each treatment arm, and 120 patients in total.

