9. RANDOMISATION/BLINDING

9.1. Randomisation

A nurse not involved in the research project performed a computer-generated block randomization, ten patients in each block. The allocation sequence was generated by a software program:

(<http://randomization.com>) and was conducted with a 1:1 ratio between the treatment arms. With 60 patients within each intervention group, twelve blocks of ten patients was needed. 120 sequentially numbered, opaque, sealed envelopes, containing a label describing one of the two interventions, were placed in the operating theatre at operation. The envelope was opened only if the patient fulfilled the inclusion criteria and the baseline assessments. One of the assisting nurses would open the envelopes at the request of the surgeon. The randomization was performed only after the ACL rupture was verified by arthroscopy, and at least 50 % of each menisci was left intact after surgical treatment, and if the hamstring graft sizes were sufficient after harvesting (the minimal desired hamstring graft sizes were 5.0 mm for the PL bundle and 6.0 mm in diameter for the AM bundle).

9.2. Level and method for blinding:

KOOS/IKDC and the activity scales: Initially, the trial participants were not intentionally blinded for the intervention, but the outcome assessor was blinded. The outcome assessor ensured that the PRO from the patients were complete.

The level of blinding was changed during the enrollment, and the study participants number 62 – 120 were consequently blinded for the intervention. Unblinding was performed after the assessments of the two-years follow-up.

Functional tests: The outcome assessor that completed the functional tests, was blinded for the intervention.

Clinical assessment: The clinical assessment was performed by the assisting, orthopaedic surgeon [name]. The surgeon was not blinded, as she was also present during the initial surgery.

Radiographic imaging: The radiologist was not blinded, as the intervention was visible at the radiographic imaging.

Data analysis: The statistical advisor will be blinded when performing the analysis.

10. STATISTICAL METHODS:

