“An adverse event refers to an untoward occurrence during the trial, which may or may not be causally related to the intervention or other aspects of trial participation” [13]. The study participants were questioned whether they had observed any adverse events related to the treatment during the last year, at the one and two-years follow-up. Each subject were counted once in each category of AE, but each participant could have more than one AE. Any repetition of the same event in one patient was ignored. Additional information about the event was obtained from the patient’s journal if necessary.

11.2.1. Events:

- Bleeding/Hematoma
- Deep venous thrombosis (DVT)
- Injury larger nerves or vessels
- Infection/Septic arthritis
- Arthrofibrosis
- Cyclops
- Donor site morbidity

11.2.2. New injury:

- Meniscal lesion
- Chondral lesion
- Graft re-rupture

11.2.3. New operations:

Because of bleeding/hematoma
Because of injury to larger vessels/nerves
Because of infection
Because of arthrofibrosis
Because of cyclops/extension deficit
Because of donor site morbidity (e.g. removal of fixation device, scar tissue)

Because of Menisci surgery
 Medial menisci resection
 Lateral menisci resection
 Medial menisci suture
 Lateral menisci suture
 Med menisci transplantation
 Lateral menisci transplantation

Because of Cartilage treatment

Because of revision surgery

Others reoperations.

12. PROTOCOL DEVIATIONS:

3.1. Study design:

The hypothesis in the original study protocol was formulated as in a non-inferiority study. Although further evaluations and sample size calculations of the study were designed as in a superiority study design, with the hypothesis questioning if the double-bundle technique was superior to the single-bundle method regarding the KOOS, QoL subscale.

Double-bundle reconstructions are considered more cost demanding, time-consuming and require higher skills of the performing surgeon compared to single-bundle surgery; therefore a superiority study was the preferred study design[22].

2.2. Secondary outcomes:

The Activity scale as one of the PROM's was added after the protocol was made but before inclusion of the first patient.

3.2. Study settings – primary endpoint:

The primary endpoint was changed from five to two-years follow-up, because of a prolonged inclusion period.

3.2. Study settings:

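### Fixation-device problems and device removal are counted inside donor site morbidity, so the safety tables give no device-related count by arm and a diluted ratio between arms

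*SAP*

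**What the plan says.** Section 7.6 lists as a single adverse event "Donor site morbidity due to fixation device, scar tissue or to the hamstrings tendon harvesting in involved leg". Section 11.2.1 carries the category forward under the same name. Section 11.2.3 gives the matching reoperation reason as "Because of donor site morbidity (e.g. removal of fixation device, scar tissue", followed by a closing bracket. No row in 7.6, 11.2.1 or 11.2.3 is reserved for implant problems. Under section 11.2 a subject counts once in each adverse-event category.

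Section 4 describes the hamstring harvest once, before the two techniques are described separately. Section 9.1 allows the envelope to be opened only "if the hamstring graft sizes were sufficient after harvesting".

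Fixation then differs by arm:
- **Single-bundle (4.1):** "graft fixation on the femoral side was obtained with a suspension device", and tibial fixation "with a non-absorbable PEEK interference screw".
- **Double-bundle (4.2):** "fixation on the femoral side was realized with one suspension device for each tunnel", and on the tibial side "Both tibial fixations were achieved with an eccentric placed PEEK interference screw".

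The secondary outcome list (6.2, item 16) uses a different term, donor site pain. In 10.3.2, item 16 names only graft failures and new meniscus injuries for testing among the adverse events, and item 17 tests reoperations.

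**The concern.** The row combines a component that the allocation can affect with one that it cannot. Harvest is finished before the arm is known, so harvest morbidity is background, equal between arms in expectation. The number of implants is part of the difference between the techniques, so device complaints and device removal bear directly on the comparison.

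The label adds to the problem. A reader who sees donor site morbidity will think of the tendon harvest, not of femoral suspension devices or tibial screws. The term in 6.2 item 16 would not naturally cover device removal either. A table could therefore show similar donor site morbidity in the two arms while a difference in device-related events sits inside the row and is never listed.

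The SAP can be more specific: 11.2.3 splits meniscal reoperations into six rows by side and procedure, while device removal appears only as an example in brackets.

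**Working it through.** **The plan's own figures.** The SAP gives no rate and no calculation for this category. The only figure needed is the size of the arms. Section 8 states 56 per group for 8 points, SD 15, 80% power and two-sided 0.05, and 60 per arm after 5% drop-out. A recalculation gives 56, and 56/0.95 = 58.9, that is 59, close to the stated 60. I use 60 per arm.

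**Implants, from 4.1 and 4.2.**
- Single-bundle: 1 suspension device + 1 screw = 2.
- Double-bundle: 2 suspension devices + 2 screws = 4, reading the tibial sentence as one screw for each of the two fixations.

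**Model of the pooled row.** Let d be the risk of a device problem and h the risk of harvest morbidity, with h equal in both arms. Assume the two are independent. Counting each subject once gives

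pooled risk = 1 − (1 − d)(1 − h)

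and so

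pooled risk difference = (1 − h) × (difference in d).

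All values of d and h below are assumptions. The twofold ratio follows implant number for illustration only; the SAP does not say that harm scales this way.

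| Device risk, single vs double | h | Pooled risk, single vs double | Risk ratio | Risk difference (points) |
|---|---|---|---|---|
| 5% vs 10% | 0 (separate row) | 5.0% vs 10.0% | 2.00 | 5.0 |
| 5% vs 10% | 5% | 9.75% vs 14.5% | 1.49 | 4.75 |
| 5% vs 10% | 10% | 14.5% vs 19.0% | 1.31 | 4.5 |
| 5% vs 10% | 20% | 24.0% vs 28.0% | 1.17 | 4.0 |
| 10% vs 20% | 0 (separate row) | 10.0% vs 20.0% | 2.00 | 10.0 |
| 10% vs 20% | 5% | 14.5% vs 24.0% | 1.66 | 9.5 |
| 10% vs 20% | 10% | 19.0% vs 28.0% | 1.47 | 9.0 |
| 10% vs 20% | 20% | 28.0% vs 36.0% | 1.29 | 8.0 |

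**In patients.** At 60 per arm, 5% versus 10% is 3 versus 6 patients with a device problem. Pooled with h = 20%, the row shows on average 60 × 0.24 = 14.4 versus 60 × 0.28 = 16.8. The excess in double-bundle falls from 3 to 2.4 patients. Most of it is still there, but it is set against a much larger background, and nothing in the row says that it concerns devices.

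**Would a test help?** None is planned for this category. For scale only, the exact power of a two-sided Fisher mid-P test at 0.05 with 60 per arm is 14% for 5% versus 10% as a separate row, and 11%, 9% and 8% when pooled with h of 5%, 10% and 20%. For 10% versus 20% it is 32% separate, and 25%, 20% and 15% pooled. A formal test would be weak with or without the split.

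**The case against.** **Implant harm becomes invisible.** A reader might infer this, but the SAP does not support it. Harvest morbidity is balanced in expectation, so the pooled risk difference keeps the fraction (1 − h) of the device difference, at least 80% of it in the cases above. What is lost is the separate count and the size of the ratio.

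**A planned safety test loses much of its power.** A reader might also infer this. If device morbidity were 5% versus 20%, the mid-P power with 57 per arm (60 less 5%) would fall from 69% to between 52% and 28% on pooling. But nothing in the SAP supports a fourfold ratio, and 10.3.2 item 16 names no test for donor site morbidity. The reoperation test in item 17 does not depend on how the reasons are labelled, since device removals count in it either way.

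**Scar is not purely pre-randomisation.** Section 4 describes one incision at the pes anserine, and no separate tibial incision is described. Tibial tunnels and screws follow allocation, so scar or discomfort there may partly reflect the technique. Grouping by anatomical site is a defensible choice for events at that incision. This stands, and it is a reason not to merge scar with harvest as background.

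**The reoperation row is less mixed.** Section 11.2.3 names device removal and scar tissue as examples, not harvest, and the once-per-category rule is stated for adverse events only. This stands. There the defect is the missing row for device removal, not dilution by harvest events.

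**Cause may not be on record.** Section 3.2 says that the last follow-up was in June 2017, and events came from questioning at one and two years with the journal used if necessary. Some events may not be classifiable. This also stands, and the fix allows for it.

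**Conclusion.** The point holds as a weakness in descriptive safety reporting. As written, 7.6, 11.2.1 and 11.2.3 yield no count of device-related morbidity or device removal by arm, although fixation hardware is a designed difference between the techniques. The pooled row also understates the ratio: an assumed 2.0 appears as 1.49 to 1.17 for device risks of 5% versus 10% and harvest morbidity of 5% to 20%, and as 1.66 to 1.29 for 10% versus 20%. The risk difference is largely preserved.

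These sizes rest on assumed rates, on independence of the two kinds of event, on equal harvest morbidity in the arms (true in expectation, not necessarily in the observed data) and on the reading of four implants in double-bundle. The absence of a separate count rests on none of these. The primary analysis and every test named in the SAP are untouched. Severity is minor.

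**What to change.** In 7.6, 11.2.1 and 11.2.3:
- Report three descriptive rows: fixation-device-related morbidity, harvest-site morbidity, and scar. Keep the pooled row as well.
- Make fixation-device removal its own reoperation reason in 11.2.3.
- Classify from the patient journal, which 11.2 already allows as a source. Where it does not settle the matter, record the cause as undetermined.
- For each row give the number of patients per arm with at least one event, and the risk difference with the 95% Newcombe interval already used in 10.3.2 items 13 and 18. No test is needed.
- Use one term throughout, so that 6.2 item 16 (donor site pain) and 7.6 and 11.2 (donor site morbidity) describe the same outcome.
- In the same revision, list septic arthritis apart from superficial infection. Sections 7.6 and 11.2.1 combine them, so the serious event has no count of its own beyond what the row for reoperation due to infection may show.

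The cost is SAP wording and some recoding from records, with no new patients, visits or procedures. The downside is small counts, wide intervals and possibly some events that cannot be classified.
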